## 1 Introduction

### 1.1 Purpose

This Primary Statistical Analysis Plan (SAP) describes analyses of the primary and secondary objectives of the TERA study. The Primary SAP outlines the general statistical approaches that will be used in the analysis of the study. It has been developed to facilitate discussion of the statistical analysis components among the study team, and to provide agreement between the study team and statisticians regarding the statistical analyses presented in the primary statistical analysis report. This analysis plan may be modified by the study team as new information becomes available outside of the study or to reflect recommendations of the SMC. In addition, some analyses may be omitted if there is insufficient information. Outlines of analyses for the other objectives will be presented in separate SAPs. Detailed outlines of tables, figures, and coding descriptions are included in a separate Analysis Implementation Plan (AIP).

The primary statistical report will be used for submission of results to ClinicalTrials.gov. Results for primary measures must be submitted within one year of the primary completion date (PCD), which for TERA is based on 12 weeks of follow-up. Results for secondary outcomes measures are due one year after follow-up is complete on all study participants.

### 1.2 Key Updates

Version	Changes Made	Rationale	Effective Date
1.0	Original Version		Dec 20, 2017
2.0	

Updated study population

Removed BID regimens

	

Responding to Protocol Version 2.0 and SMC suggestions from June 2018 review

No changes needed for Protocol Version 3.0

	April 4, 2019
3.0	

Changes to analysis due to COVID outbreak

Updates to secondary outcome measures

Clarification of how deaths are handled in virologic outcome measures

	

Responding to changes in follow-up due to COVID outbreak

	June 24, 2020

## 2 Protocol Overview

### 2.1 Study Design

TERA is a Phase II, randomized, open-label study designed to assess the effectiveness of a Triggered Escalating Real-Time Adherence (TERA) intervention for 12 weeks in Youth Living With HIV (YLWH) failing antiretroviral therapy (ART). This time-limited approach includes education and motivational skills building from an adherence coach and monitoring with wireless electronic dose monitoring (EDM), for identification of delayed and missed doses of antiretrovirals and related alerts and coach phone-based outreach.

The original design was to enroll 120 YLWH, stratify by age (<18 years vs.  $\geq$ 18 years), and randomize with equal probability to TERA or continuing standard-of-care (SOC) for adherence. At entry, half were randomly selected to engage in additional in-depth interviews about their experiences at Weeks 12 and 48, with the goal of having 40 evaluable participants at both time points. Participants were followed for 48 weeks.

In August 2019, the Adolescent Trials Network Safety Monitoring Committee (SMC) recommended that accrual be closed and the 89 enrolled participants continue follow-up to study completion.

In March 2020, study visits were paused due to the outbreak of COVID-19. The study team decided to use the 'pre-COVID' database to analyze the primary and secondary objectives, since data collected after study visits resumed would be inherently different. This required a change to the definition of the virologic secondary outcome measures. It also meant that sample sizes at later study visits would be lower than anticipated, with a corresponding reduction in power to detect differences between arms. Additional data may be collected at study visits that take place after sites re-open. Analysis of these data will be outlined in a separate SAP.

### 2.2 Hypotheses

1. Youth in the TERA arm will be more likely to achieve viral suppression at Weeks 12 (primary), 24, 36 and 48 compared to youth in the SOC arm
2. Youth in the TERA arm will be more likely to achieve and sustain viral suppression than those in the SOC arm
3. Youth in the TERA arm will have higher rates of weekly dosing as measured by EDM over 48 weeks than those in the SOC arm
4. Viral suppression and adherence will be associated with gains in adherence-related information, motivation and behavioral skills, which will be higher in youth in the TERA arm than those in the SOC arm
5. Youth will report positive attitudes and experiences with the intervention on interview with themes emerging relative to adherence support that are unique from those in the SOC arm.

### 2.3 Objectives

Primary Objective:

1. To estimate and compare HIV virologic suppression rates in YLWH 12 weeks after initiating TERA or continuing SOC.

Secondary objectives:

1. To estimate and compare virologic suppression rates in YLWH 24, 36, and 48 weeks after initiating TERA or continuing SOC
2. To estimate and compare proportions of participants initiating TERA or continuing SOC who achieve virologic suppression (HIV-1 RNA < 200 copies/ml) by 12 weeks and maintain virologic suppression through 48 weeks
3. To summarize and compare adherence patterns in YLWH initiating TERA or continuing SOC during on-intervention period (week 0-12) and post intervention period (week >12-48).

### **3 Definitions**

“Study entry” is defined as the randomization date. The value used for baseline summaries will be the last evaluation on or before the randomization date.

Any youth found to be ineligible or who the Core Team determine should not be included in any analyses, will be included in screening, accrual and eligibility summaries only. Otherwise, analyses will be intent-to-treat (ITT), including all eligible participants randomized to the study and by randomized arm, regardless of compliance to the TERA intervention, SOC, or ART regimen.

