## 7 Report Components

Detailed descriptions of the content of each of the following sections are given in the AIP.

1. Study entry
  - a. Screening
  - b. Accrual
  - c. Eligibility and stratification errors
2. Baseline characteristics
  - a. Demographics
  - b. Sexual identity
  - c. Sex behavior
  - d. Substance use
  - e. Life events
  - f. HIV cascade
  - g. Health status
  - h. Mental functioning
  - i. HIV stigma
  - j. Adherence
  - k. Antiretroviral medication history
  - l. Psychotropic medications
3. Study and intervention status
4. Data completeness and study implementation
5. Adverse Events and Serious adverse events
6. Changes in antiretrovirals
7. Changes in CD4 counts and %
8. Adherence support during trial participation (participant-level)
9. Primary outcome measures
10. Secondary outcome measures

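### As worded, the Section 3 exclusion would keep any randomized participant later found ineligible, or excluded by the Core Team, out of the adverse event and SAE summaries

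*SAP*

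**What the plan says.** SAP Section 3 (Definitions) names two groups: "Any youth found to be ineligible or who the Core Team determine should not be included in any analyses". It then says where they appear: they "will be included in screening, accrual and eligibility summaries only". The following sentence makes everything else intent-to-treat, "including all eligible participants randomized to the study and by randomized arm".

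Section 7 lists the parts of the primary report. Item 1 (study entry) covers screening, accrual and, as 1c, "Eligibility and stratification errors". Item 5 is a separate part, "Adverse Events and Serious adverse events", given as a bare heading with no population of its own. The section adds that "Detailed descriptions of the content of each of the following sections are given in the AIP".

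Section 1.1 says of the report: "The primary statistical report will be used for submission of results to ClinicalTrials.gov".

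**The concern.** Ineligibility can be a reason to restrict an efficacy population. It is not a reason to leave out harms that occurred after randomization, while the participant was assigned to TERA or standard of care. The Section 3 rule does not distinguish the two purposes: it gives one list of permitted summaries, and adverse events are not on it.

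At stake is the completeness of the AE and SAE tables in the report that feeds public results submission. Both the event counts and the number of participants at risk would be short by anyone removed under the rule. The second route to exclusion, a Core Team decision, has no stated criteria or timing in Section 3, and Section 2.1 describes the trial as open-label. An exclusion could therefore be decided after an event is known. Nothing suggests that this was done or intended, but the wording leaves it possible.

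**Working it through.** The SAP states no figure that could be reproduced here. The check is mainly a reading of the sections against each other.

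1. **Does the rule reach randomized participants, or only screen failures?** It covers screen failures, for whom it is ordinary and harmless. It also appears to cover randomized participants, for two reasons. Section 3 restricts the ITT set to those who are both eligible and randomized, a restriction needed only if someone can be randomized and ineligible. Section 7 item 1c plans a summary of eligibility errors next to stratification errors, and the latter arise at randomization. Section 4.2 adds that screening and entry may fall on the same day, so it is plausible (an inference) that some ineligibility comes to light only afterwards.

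2. **Is the rule limited to efficacy?** No. The exclusion clause speaks of analyses in general, and the word that closes the list of permitted summaries has no exception.

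3. **Does the AE/SAE section fall within the permitted summaries?** No. Screening, accrual and eligibility are in item 1; adverse events are in item 5.

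4. **Is there a safety population elsewhere that would override this?** Not in the SAP. Its only rules for deaths concern the virologic outcomes (Sections 4.3, 5, 6.1 and 6.2, where deaths unrelated to HIV are excluded) and the adherence imputation (Section 6.3.1). Neither governs item 5.

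5. **How large could the effect be?** The one usable input is the enrolment in Section 2.1: "the 89 enrolled participants continue follow-up to study completion". Section 2.1 gives equal randomization probability, so assume a near-equal split: 89 / 2 = 44.5, that is, 44 in one arm and 45 in the other. One participant removed is then 1/44 = 2.3% or 1/45 = 2.2% of the arm, about 2%. The number of participants removed and the number of events they had are not given, so the effect on any reported rate cannot be estimated.

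**The case against.** The strongest reply is that the SAP may not be meant to fix the safety population at all. Section 1.1 says that it covers the primary and secondary objectives, and none of those in Section 2.3 concerns safety. Item 5 is only a heading, and table detail is left to the Analysis Implementation Plan, which is not at hand and could define a safety set. This lowers the certainty about what the final tables will contain. It does not remove the point: the AIP is described as giving the content of report sections, not as replacing the populations set in Section 3. An AIP that included these participants would contradict the SAP's wording, which would then still need correcting.

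A second reply concerns importance. The intervention is education, coaching, dose monitoring and phone outreach. A Safety Monitoring Committee oversees the trial, and nothing in Section 3 limits what it sees. No primary or secondary estimate changes. All of this stands, and it keeps the point to a correction of the report's safety summaries.

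A reader might also infer more than the SAP supports:

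- *That safety data have been lost.* The SAP gives no count of participants who were randomized and ineligible, and reports no event in such a participant.
- *That a reported SAE rate would be halved or otherwise distorted by a known amount.* Any such example would rest on invented event counts.
- *That the omission would be invisible.* The excluded youth stay in the accrual and eligibility summaries, so a reader of the full report could compare accrual with the AE denominator and see that participants are missing. Their events would still not be shown.
- *That deaths are lost as a category of their own.* Section 7 plans no separate deaths table, so deaths are affected only through SAE reporting.

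**Conclusion.** The point holds as a defect of wording with a conditional consequence. Applied as written, Section 3 would remove any randomized participant later found ineligible, or excluded by the Core Team, from both the counts and the denominators of the AE and SAE summaries. Each would be about 2% of an arm under an equal split of the 89 enrolled. The total effect is unknown and may be zero.

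This rests on two assumptions: that the Section 3 rule governs all parts of the primary report, as its unqualified wording indicates, and that the AIP does not depart from it. It concerns the aggregate tables of the report only; it does not imply that events went unreported to oversight bodies. The correction is worth making because it is simple and the tables go into a report used for public results submission.

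**What to change.** In Section 3, limit the exclusion sentence to the primary and secondary outcome analyses. Add that the AE and SAE summaries (Section 7, item 5) include all randomized participants by randomized arm, using whatever safety data were collected, and that any participants excluded from the outcome analyses are identified there. The AIP should carry the same population.

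The SAP does not say whether youth found ineligible stayed in follow-up, so the wording should neither promise complete data for them nor introduce a new safety observation period.

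The cost is a short text change and a population flag. The drawback is that safety and efficacy denominators may differ by a few participants, which a footnote can explain. No efficacy or adherence result changes, and if no randomized participant was excluded, the tables stay the same.

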### **4 Statistical Methods**

#### **4.1 General considerations**

Baseline characteristics will be summarized by arm, but with no statistical comparisons. In general, categorical data will be summarized using N (%) and continuous data using N, key quantiles, and mean (STD) when appropriate.

Because of the interruption in study visits due to the COVID-19 pandemic in March 2020, analyses of the primary and secondary objectives will use the ‘pre-COVID’ study database including all data collected before study visits were paused. By March 2020, all participants had had the opportunity to reach Week 12, so analyses of the primary outcome measures were unaffected. However not all participants had had the opportunity to reach the Week 24, 36 and 48 timepoints. Only participants with the opportunity to reach each timepoint prior to the COVID-19 study pause will be included in assessments of the secondary outcome measures.

As this is a Phase II study, there are no *a-priori* statistical stopping guidelines. Statistical tests (all two-sided) will not be adjusted for interim monitoring, multiple comparisons or stratification for age. Significance levels  $p < 0.05$  will be highlighted in the text, but must be interpreted with caution since there will be many tests. Any changes to outcome measures after the analysis has begun will be identified as *post hoc*.

This Phase II clinical trial is not subject to NIH requirements that primary analyses of intervention comparisons be summarized by sex and race.

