24 ( $\pm$  28 days) and Week 36 ( $\pm$  28 days) HIV-1 RNA measurements is < 200 copies/mL. Participants will be classified as failures if (1) either of the Week 12 or 48 HIV-1 RNA measurements are  $\geq$  200 copies/mL, (2) HIV-1 RNA at both Week 24 ( $\pm$  28 days) and Week 36 ( $\pm$  28 days) are  $\geq$  200 copies/mL, (3) both the HIV-1 RNA measurements between Weeks 12 and 48 are missing, or (4) either or both the Week 12 and Week 48 HIV-1 RNA are missing.

3. To summarize and compare adherence patterns in YLWH initiating TERA or continuing SOC during on-intervention period (week 0-12) and post intervention period (week >12-48).

Outcome measures:

- i. Electronic dose monitored adherence: Percent of days with dose taken per week
- ii. Electronic dose monitored on-time adherence: Percent of days with dose taken within the defined acceptable windows ( $\pm$  4 hours) per week.
- iii. Electronic dose monitored non-persistence: Number of gaps (at least 7 consecutive days (168 hours) between doses) in the intervals: week 0-12, >12-24, >24-36 and >36-48.

## 5 Primary outcome measure analysis: short term virologic success at Week 12

The primary objective of the study is to estimate and compare HIV virologic suppression rates (HIV-1 RNA < 50 copies/ml and <200 copies/ml) 12 weeks after initiating the TERA intervention or continuing SOC. If more than one HIV-1 RNA measurement occurs within the allowable 28-day window, the highest value will be chosen. Other than participants dying for reasons unrelated to HIV before Week 12, all eligible participants will be included in this analysis, classifying those lost-to-follow-up as failures. Sensitivity analyses will repeat the primary analysis (i) using observed HIV-1 RNA only (participants with missing week 12 HIV-1 RNA not included in denominator), (ii) using a wider window around the Week 12 study visit, and (iii) using last observed HIV-1 RNA if missing week 12.

Virologic success rates in each arm and the difference in success rates between arms will be summarized with 95% confidence intervals (CIs). Analyses adjusting for covariates identified *a priori* by the study team will be conducted to assess whether the magnitude and strength of the association between the intervention and virologic success changes after adjustment for other factors.

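### Randomisation is stratified by age, but SAP Section 4.1 keeps the stratum out of the tests, so the Week 12 comparison is conservative and loses power if age is strongly prognostic

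*SAP*

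**What the plan says.** Section 2.1 describes the randomisation: "The original design was to enroll 120 YLWH, stratify by age" (under 18 versus 18 years and over), and "randomize with equal probability to TERA or continuing standard-of-care (SOC) for adherence". Age is the only stratification factor named. Accrual closed at 89 of the 120 planned participants.

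Section 4.1 states that all tests are two-sided and "will not be adjusted for interim monitoring, multiple comparisons or stratification for age". It gives no reason for leaving out the stratum. The Phase II status mentioned there is attached to the absence of stopping guidelines.

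Section 5 reports the Week 12 success rates by arm and their difference with 95% confidence intervals. It names neither a test nor an interval method. It adds "Analyses adjusting for covariates identified" in advance by the study team, but does not list the covariates, so whether age is among them is open.

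Section 7 plans a report item on "Eligibility and stratification errors", so the stratum is on record for each participant.

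**The concern.** Section 4.1 puts unlike decisions in one sentence. Forgoing a multiplicity adjustment accepts more false positives in return for power, which is a recognised Phase II choice. Ignoring a stratification factor brings no comparable gain. The design forces the two arms to have nearly the same age mix, so the arm difference varies less from trial to trial than under simple randomisation. An unstratified standard error does not know this and still includes the between-age variation. If age predicts suppression, the test runs below its nominal level and the interval is too wide.

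Week 12 suppression is the primary outcome, and at most 89 participants contribute to it: Section 3 removes ineligible youth and Section 4.3 removes deaths unrelated to HIV before Week 12. The design bought some precision by stratifying. The stated rule discards it in a trial already smaller than planned. That the confidence interval is unstratified as well is an inference, because Section 4.1 speaks of tests and Section 5 names no interval method.

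**Working it through.** The SAP gives no power statement, assumed rates or stratum sizes, so there is no figure of its own to reproduce. The check is a large-sample formula followed by simulation.

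**Inputs from the SAP:** two age strata, 1:1 allocation, N = 89, two-sided 5% level.

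**Assumed, not in the SAP:** the share in each stratum, suppression rates by age group, the true arm difference, permuted blocks of 4, and the Pearson chi-square as the unstratified test.

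**Step 1: formula.** Let *s* be the share in one stratum, *c1* and *c0* the success rates in that stratum and the other, and *p* = *s·c1* + (1 − *s*)·*c0*. The share of outcome variance explained by age is

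R² = *s*(1 − *s*)(*c1* − *c0*)² / [*p*(1 − *p*)]

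and the true type I error of the unstratified test is about 2·[1 − Φ(1.96/√(1 − R²))].

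- 20-point gap (*s* = 0.35, rates 0.45 and 0.25): *p* = 0.32, R² = 0.0091/0.2176 = 0.042, type I error 4.5%.
- 40-point gap (*s* = 0.35, rates 0.60 and 0.20): *p* = 0.34, R² = 0.0364/0.2244 = 0.162, type I error 3.2%.

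**Step 2: simulation at N = 89.** There were 40,000 trials per scenario, with 30% or 45% aged under 18 and SOC rates between 15% and 55%. The higher rate was placed in either age group. True differences were 0 (for type I error) and 20, 25 and 30 points (for power).

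| Gap in SOC suppression between age groups | Type I error, chi-square | Type I error, CMH | Power, CMH minus chi-square (points) |
|---|---|---|---|
| 0 | – | – | −1.3 to −0.4 |
| 10 | – | – | −0.4 to +0.1 |
| 20 | 4.6–4.8% | 4.9–5.1% | +0.2 to +0.8 |
| 30 | 4.0–4.2% | 4.9–5.1% | +1.1 to +3.0 |
| 40 | 3.2–3.7% | 4.8–5.0% | +3.1 to +5.8 |

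At the 40-point gap and a true difference of 25 points, power is 69–71% for chi-square and 73–76% for CMH.

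**Step 3: intervals.** At the 40-point gap the unstratified Wald standard error is 7–9% above the true standard deviation of the arm difference. Coverage of the 95% score interval there is 96.4–97.0% unstratified and 95.0–95.2% stratified (Miettinen-Nurminen variance, Mantel-Haenszel weights). A simple stratified Wald interval covers only 93.5–94.4% at any gap, so the choice of stratified interval matters.

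**Step 4: second simulation on a different scale.** This used a common odds ratio of 3, stratum shares of 20%, 35% and 50%, and 200,000 trials per scenario at N = 89.

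- Equal rates (0.30/0.30): power is equal to within 0.1 point.
- 0.25/0.45: CMH gains 0.3–0.4 points.
- 0.20/0.60: CMH gains 3.5–4.7 points (for share 35%, 64.1% versus 59.8%). Unstratified type I error is 3.4–3.7%.
- 0.10/0.70: CMH gains 14–19 points. Unstratified type I error is 1.5–1.6%. This gap is extreme and serves only as an outer limit.

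**Step 5: later visits.** At an assumed N = 50, with 15–45% aged under 18 and a true difference of 25 points, the power change from stratifying ranged from −3.9 to +3.0 points over gaps of 0 to 40. Sparse strata can make stratification costly there.

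**The case against.** The strongest reply is that nothing here is invalid. Section 4.1 states its choice openly and in advance, the estimate is unbiased, and the test errs on the safe side. The harm needs age to be strongly prognostic, which the SAP neither says nor implies. Every participant is a young person failing therapy, and Section 4.3 counts a missing Week 12 value as failure. If missingness were similar across ages, that rule would narrow any age gap. A gain of more than about 3 points needs a gap near 40 points, and at 20 points or less the choice hardly matters. The adjusted analyses in Section 5, or the separate Analysis Implementation Plan, may already include age. Section 4.1 asks for p-values to be read with caution, so no decision hangs on one test. Changing the main method late in an open-label trial has a cost of its own.

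Much of this stands. The age effect is unknown, the loss is small unless the effect is strong, and a late change must be documented. What does not stand is that the SAP already deals with the point. Section 4.1 expressly excludes the stratum from the tests. The Section 5 adjusted analyses name no covariates and are there to see whether the association changes, not to provide the main comparison. The emphasis on intervals does not help either, because an unstratified interval is too wide for the same reason.

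**Conclusion.** The concern holds. The SAP randomises within age groups and then instructs the analyst to ignore them, without giving a reason. The consequence is lost efficiency, not bias or excess false positives.

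The trade is lopsided. At N = 89, stratifying costs about 0.4–1.3 points of power if age does not matter. It gains 1.1–3.0 points at a 30-point age gap and 3.1–5.8 points at 40. These figures rest on assumed stratum shares, suppression rates, block size and comparator test. They cannot be narrowed from the document, so confidence in the actual loss is medium. The change should be made, but the planned analysis would remain valid without it. The case is for Week 12; it does not carry over automatically to later visits with fewer participants.

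**What to change.** - In Section 4.1, delete the words that exclude age stratification from the tests.
- In Section 5, for both the 50 and 200 copies/ml thresholds, make the main comparison the Mantel-Haenszel risk difference stratified by age group. Give it a stratified score-type 95% interval (not Wald) and a CMH test. Keep the unstratified result as supportive.
- Use the stratum as randomised, and repeat with actual age group if stratification errors occurred.
- Name age group among the covariates for the Section 5 adjusted analyses. If the main comparison is left as it is, this one line is the minimum.
- At Weeks 24, 36 and 48 and for sustained suppression, use the stratified method only where strata are not too sparse; otherwise report it as supportive.
- No change is asked for the logrank or GEE adherence analyses, which were not examined.

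The cost is SAP wording and minor code, with no new data. SAP version 3.0 is dated June 24, 2020, after every participant could have reached Week 12, and the trial is open-label, so the change needs a dated justification. Section 4.1 already sets a labelling rule for outcome measures: "Any changes to outcome measures after the analysis has begun will be identified as" post hoc. The same label should be applied to this change of method if analysis has begun.
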